5.3.2. Ethical Considerations

Prior to initiating enrollment at each clinical site, the informed consent document will be reviewed by the Steering Committee, Project Office, OSMB, and the Institutional Review Board (IRB) at each clinical site to insure that the document is consistent with study protocol, federal regulations, and individual institutions' policies. Enrollment will not commence until this

document has been approved by the Steering Committee, OSMB, Project Office, and each clinical site's IRB.

Participants in this study will receive an informed consent document thoroughly describing the study procedures, including the risks associated with these procedures, the amount of time required to complete study-related procedures, and the expected length of follow-up for the study. An investigator-designated research professional will review the informed consent document with each participant to insure he or she understands the study procedures and is aware of his or her rights.

5.3.2.1. Special Ethical Issues

Smoking Cessation

All enrolled participants who smoke will be provided with information about smoking cessation and, where available, referred to cessation programs.

Hold on Bronchodilator and Anticholinergic Therapy

In order to obtain accurate measurements of lung function, participants will need to abstain from using inhaled bronchodilators (e.g., albuterol) for six hours prior to pulmonary function testing and inhaled anticholinergics (e.g., ipratropium) for eight hours prior to pulmonary function testing. It will be at the discretion of the investigator as to whether it is medically advisable for a participant to abstain from bronchodilator therapy. Practicality may require some long-acting bronchodilators to simply be noted rather than withheld.

Genetics

SPIROMICS will be collecting specimens for and conducting analyses of genetic information on all participants. Strict confidentiality standards are in place and will be maintained to protect the privacy of SPIROMICS participants. Biospecimen samples will be labeled with a unique identifier that does not contain any protected health information or otherwise identifies a participant.

In the event a new genetic marker is found during the course of SPIROMICS, participants with this hypothetical marker will not be notified. The analyses conducted as part of SPIROMICS are not intended to be diagnostic, and may not take place in a Clinical Laboratory Improvement Amendments (CLIA) certified lab. Some ancillary studies, however, may conduct genetic or other analyses in CLIA labs and may potentially include participant notification as part of the study protocol.

Specimen Storage for Future Studies

Some of the biospecimens collected as part of this study will be stored for future analyses. These specimens will not be individually identifiable by the laboratory or GIC personnel. The GIC will develop and maintain a tracking system whereby study participants can modify their level of consent. Participants can ask that any specimens still in storage be destroyed and not included in future analyses. The request to remove stored specimens will be made at the clinical centers to preserve participant confidentiality.

5.3.3. Participant Recruitment Plans and Consent Process

5.3.3.1. Internal sources

Patient referrals

Participants will be recruited from the patient population at each clinical center. Patients may be referred by their physician to study personnel or study personnel may, after obtaining permission from a patient's physician, approach patients directly regarding interest in the study. Study personnel may use the SPIROMICS Introductory Letter and/or SPIROMICS study pamphlet (both available on study website: www.csc.unc.edu/spir) when contacting potential participants.

5.3.3.2. External sources

Clinical centers may solicit participants using posters or /flyers, email lists, and print media that comply with the official study template (available on study website: www.csc.unc.edu/spir). It is important that any communication to potential participants be approved by the clinical center's IRB and comply with any institutional requirements. Flyers can only be placed in locations where they will be seen by individuals seeking medical care (e.g., doctor's office, pulmonary rehabilitation clinic). Flyers should not be placed in public locations, such as elevators or cafeterias.

Potential participants may self-refer via the SPIROMICS study website (www.spiromics.com). In the event that the GIC receives questions regarding participation in the study, the individual will be referred to the appropriate clinical center.

5.3.3.3. Consent Process

In order to participate in SPIROMICS individuals must be willing to participate in a research study and meet the eligibility criteria outlined in Table 2. Clinical center staff will provide a copy of the informed consent form to individuals who meet these criteria and allow them an opportunity to read the document. Staff members will then review the document with the potential participants, verbally explaining each section of the informed consent and answering any questions. If at the end of this review an individual feels comfortable proceeding, the clinic staff member will obtain the participant's signature. Clinic staff will also sign the consent form. A copy of the signed form will be given to the participant and the original will be stored by the clinical center.

With respect to the Health Insurance Portability and Accountability Act of 1996, IRBs generally require that informed consent documents describe the following information for participants:

1. Procedures that are followed to keep participant information, specimens, and tissues confidential.
2. A description of what information could be seen by researchers or other people (such as members of the DSMB, FDA)
3. A description of why researchers or other people would need to see this information.
4. A description of what happens to information after the study is over or if the participant leaves the study before it is finished

5. A description of when a participant's permission expires

In addition, participants will be asked if they would like to be contacted for future ancillary studies related to SPIROMICS. Please see the study website (www.csc.c.unc.edu/spir) for the most current version of the Ancillary Studies Policy.

5.3.4. Risks to Participants

5.3.4.1. Clinical sites

There is a risk that someone not authorized to view participant information, including identifiable information, will gain access to this information. Clinical sites will take measures to prevent this from happening and will comply with local regulations. Risks related to individual procedures performed as part of SPIROMICS are included for each assessment starting in Section 6.4.

5.3.4.2. GIC

The only direct risk to participants originating from the GIC is the risk of breach of confidentiality. The GIC has many safeguards against this, including staff training, controlled access to computer and paper files, back up systems for electronic data, and protection against malicious code. More detail regarding the GIC's security plans and measures is available in Section 8 of this protocol: Data Handling and Record Keeping.

5.3.4.3. Change in or loss of insurance coverage

There is a risk that a participant may experience change in coverage, change in cost, or loss of insurance as a result of incidental findings during the course of the study. Tests performed as part of the SPIROMICS study are for research purposes only, and are not for clinical or diagnostic use. Therefore, the results of these tests will not be reported to insurance companies.

During the course of a study-related procedure, it is possible that a previously unknown disease or illness will be discovered (e.g., cancerous growth found during CT scan) or that a change in disease severity will be found (e.g., decreased lung function). If one of these two events occurs, the participant will be referred to care outside of the SPIROMICS study. The resultant diagnosis and care may result in changes to a participant's insurance.

5.3.5. Benefits to Participants

No direct benefits to the study participant are expected to result from participation in the proposed study, as will be stated in the informed consent. Potential benefits to the study participant may result if the clinical center examination and the measurements associated with it identify a health problem previously unknown to the affected individual.

Benefits to the COPD patients and to society are expected to accrue from the proposed research. The knowledge gained in this study will be used to develop methods of classifying

pathogenically homogeneous subpopulations of COPD patients for the purpose of targeting specific pathogenic processes. A second goal is to identify markers of disease progression and treatment response that will be useful for monitoring a patient's progress during a period of less than one year. These aims, if successful, would allow a targeted approach to disease treatment on an individual basis.

5.3.6. When and How to Withdraw Participants

5.3.6.1. Principal Investigator (PI) Discretion

A study participant can be withdrawn from the study if the clinical center PI determines that it is unsafe or unethical for the participant to continue in the study. Situations that might result in this kind of withdrawal include:

- bodily impairment such that the participant cannot complete the study protocol
- institutionalization (e.g., long-term care facility, prison)
- aggressive or antagonistic behavior towards clinical center staff

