2.1.2. COPD as a systemic disease

It is now appreciated and accepted that COPD is associated with important systemic, extra-pulmonary symptoms, especially in patients with more advanced disease (Couillard et al 2010, Papaioannou et al, 2009). Although the underlying mechanisms of these systemic effects are still under investigation, they are thought to be due to persistent inflammatory disease, imbalanced oxidative stress, or abnormal immunological function. Many patients with COPD have decreased fat-free mass, impaired systemic muscle function, anemia, osteoporosis, depression, pulmonary hypertension, and cor pulmonale, all of which can contribute to outcome. Indeed, dyspnea, body mass index, and timed six minute walk distance have been reported to be better predictors for mortality than lung function tests, such as FEV₁. Understanding these systemic aspects of COPD is clearly important for a complete phenotypic classification of COPD in the individual patient.

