Another targeted approach to subgroup finding corresponds to prospectively identifying components of COPD syndrome that are associated with a worse prognosis, as measured by morbidity over a 3-year study period, when compared to participants without those components. The longitudinal study design allows an evaluation of subgroups defined at baseline or during the first year of follow-up with respect to long-term outcomes such as number and severity of exacerbations and decline in FEV₁.

The statistical analysis plan for evaluation of this aim is described in greater detail in Section 7,

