6.6. Safety and Adverse Events

6.6.1. Participant Safety

It is expected that some participants will experience changes in disease severity, will develop comorbidities to COPD, and/or will expire during the course of participating in SPIROMICS. SPIROMICS staff will provide appropriate referrals for medical care if during study visits clinically relevant changes in disease status are found. SPIROMICS is not a treatment trial and as such will not report the above listed events as adverse or serious adverse events as they are considered the natural progression of COPD.

Adverse events that result directly from study procedures, including those risks outlined in each procedure section and any not listed in this document, will be reported to the Steering Committee and OSMB.

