6.7.1.2. National Death Index

The National Death Index will be annually searched to determine if any participants lost to follow-up have died. If a participant is found on this list, the death certificate and any associated hospitalization records will be requested, and the Death CRF submitted. The National Death Index will also be queried at the completion of the study.

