7.4.3. Intermediate Outcome Identification and Initial Validation

Validating biomarkers or surrogate endpoints is quite challenging, especially if the goal is to satisfy the Prentice criteria for surrogate validity (Prentice, 1989). The Prentice criteria demand two conditions of a surrogate S for a primary endpoint T : (1) that S and T be correlated (i.e., not independent) and (2) that a test of the null hypothesis of no treatment effect on S is equivalent to a test of the null hypothesis of no treatment effect on T . In applying the Prentice criteria,

candidate surrogates are first screened relative to condition (1) by examining the correlation between the candidate surrogates and clinical endpoints of interest. The primary clinical endpoints in SPIROMICS are all-cause mortality, exacerbations, and decline in FEV₁, over three years. In addition, baseline measures such as initial FEV₁ will be used as secondary measures for surrogate candidate discovery. At the second stage, a test of condition (2) is carried out. With novel surrogate candidates, such as those anticipated for SPIROMICS, sets of completed clinical trials are likely not available. The approach planned here is to view differences among disease severity categories and controls as analogues of treatment group differences, and proceed with screening candidate surrogates using the methods of Daniels and Hughes (1987) for condition (2). The design of SPIROMICS is observational, involving no randomized conditions. Thus any findings of association between clinical endpoints and candidate surrogates will not establish causality of disease severity on the biomarker (or vice versa). However, association of a potential surrogate (or changes in the surrogate) with clinical endpoints occurring prospectively in the study will offer powerful evidence of the potential utility of the surrogate for future trial design.

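### Investigator withdrawal for impairment or long-term care has no procedures-only status, so later hospitalizations and exacerbations may be missed in the sickest participants

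*Protocol*

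**What the plan says.** **Withdrawal.** Section 5.3.6.1 permits withdrawal from the study "if the clinical center PI determines that it is unsafe or unethical for the participant to continue in the study". Among situations that might lead to this it lists "bodily impairment such that the participant cannot complete the study protocol" and "institutionalization (e.g., long-term care facility, prison" (the closing bracket follows in the source). The third example is hostile behaviour towards staff.

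**After withdrawal.** Section 5.3.6.2 offers partial options, but for withdrawal at the participant's request, and they concern the use of data and specimens. The exit interview in 5.3.6.3 applies when the participant chooses to leave. No section describes reduced follow-up after withdrawal by the investigator.

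**Disease course.** Section 2.1.2 states: "Many patients with COPD have decreased fat-free mass, impaired systemic muscle function". Section 6.6.1 expects severity changes, comorbidities and deaths during participation, and does not report them as adverse events because "they are considered the natural progression of COPD".

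**Endpoints.** Section 7.4.3: "The primary clinical endpoints in SPIROMICS are all-cause mortality, exacerbations", together with FEV₁ decline over three years. Primary Aim 1 (3.1.1) includes finding "components of COPD syndrome that are associated with a worse prognosis, as measured by morbidity over a 3-year study period".

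**Ascertainment.** Hospitalizations are self-reported at visits and quarterly calls, then documented from records that the participant releases (4.1.1.1, 6.7.2.2). Milder exacerbations are counted from participant report (4.1.1.2, 6.5.1). Deaths come from visits, calls and proxies (6.7.1.1) and from the registry: "The National Death Index will be annually searched to determine if any participants lost to follow-up have died". Section 6.7.1.2 adds a further Index query at study completion.

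**The concern.** The withdrawal examples combine two different acts: stopping procedures that a person can no longer do, and ending the counting of that person's events. The first may be unavoidable. The second is not, because mortality and exacerbations can be ascertained without a clinic visit.

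If follow-up ends because the participant became too impaired or entered long-term care, the end of observation is related to the outcome. The events most likely to be missed are those of participants whose disease is worsening. That would weaken the prognostic contrasts between subgroups sought under Aim 1 and the marker-to-endpoint associations sought under Aim 2. Because the decision is left to each site's investigator, the extent of the loss could also differ by site.

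**Working it through.** **Step 1. What survives a withdrawal by the investigator?**

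| Endpoint | Source in the protocol | Clinic visit needed? | After withdrawal by the investigator |
|---|---|---|---|
| Hospitalization (severe exacerbation) | Self-report at visit or call, then released records | No, but contact is needed | No continuation stated, no registry back-up |
| Mild or moderate exacerbation | Self-report at visit or call | No, but contact is needed | No continuation stated, no back-up |
| Death | Visit, call, proxy, Index search | No | Annual search is for those lost to follow-up; completion query has no stated scope |
| FEV₁ decline | Spirometry at visits | Yes | Lost in any case |

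The avoidable loss is in the first two rows. The third is an ambiguity.

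**Step 2. What is at stake for exacerbations?** Section 7.1 assumes 1.5 exacerbations per year in the Severe stratum and 1.0 in Mild/Moderate. At those averages, each unobserved person-year removes 1.5 or 1.0 expected events. Adjusting a Poisson model for follow-up time would correct for the shorter observation. It would not correct for a higher rate after withdrawal than in comparable participants who remain. The document gives neither the number of such withdrawals nor their later event rate, so the bias cannot be computed. The 92% retention assumed for this endpoint is the same in both strata and makes no allowance for severity-related loss.

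**Step 3. Reproduce the stated mortality power.** Inputs from 7.1: 10% of 1,500 against 15% of 600, two-sided alpha 0.05.

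- Pooled rate = (150 + 90)/2,100 = 0.1143, matching the 240 expected deaths.
- SE under the null = √[0.1143 × 0.8857 × (1/1,500 + 1/600)] = 0.01537.
- SE under the alternative = √[0.10 × 0.90/1,500 + 0.15 × 0.85/600] = 0.01651.
- Power = Φ[(0.05 − 1.96 × 0.01537)/0.01651] = 88.6%, against 88% stated.

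At 92% retention the same formula gives 86.0%. The stated figure thus corresponds to essentially complete vital status.

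**Step 4. Worst case for mortality.** Assume that no death after such a withdrawal is ever found. The withdrawal fractions and the mortality among those withdrawn are assumptions; none is in the document. Withdrawn participants are removed from numerator and denominator.

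| Withdrawn, Severe / Mild-Moderate | Deaths missed if 50% die | Power if 50% die | Power if 30% die |
|---|---|---|---|
| 3% / 1% | 9 + 7.5 = 16.5 | 79.6% | 85% |
| 5% / 1% | 15 + 7.5 = 22.5 | 64.3% | 80% |
| 8% / 2% | 24 + 15 = 39 | 46.1% | 74% |

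Keeping withdrawn participants in the denominator as survivors lowers the 50% column to 75%, 53% and 30%. With the literature mortality rates that 7.1 cites (about 25% against 13%, or 30% against 18%), power stays above 99% in all three scenarios, even with 50% dying. If the Index covers these participants, the loss is near zero in every row.

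**The case against.** The strongest reply is that the protocol does not make worsening COPD a reason to withdraw anyone.

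- Withdrawal needs a judgement that continuing is unsafe or unethical, and the examples only illustrate when that might arise.
- Section 6.6.1 answers clinically relevant change with referral.
- Inability to do a single test is handled procedure by procedure, for example for the six-minute walk (6.4.1.2.2), anthropometry (6.4.2.2.2) and sputum induction (6.4.6.2.2).
- Institutionalization as a ground is consistent with the entry criteria in Table 2.
- Section 5.3.6.1 does not say that calls or record requests must cease.

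Most of this stands. A reader might infer that the fastest progressors will leave and that their deaths go uncounted. The documents do not support that. Withdrawal is discretionary and conditional. The annual Index search may well treat these participants as lost to follow-up, and the completion query carries no such restriction.

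A reader might also infer that mortality power falls to 80%, 64% or 46%. Those figures require assumed withdrawal rates, 50% mortality among the withdrawn and no Index capture. Section 7.1 also presents the strata comparison as illustrative, and the proportional hazards analysis in 7.4.1 would keep the time observed before withdrawal.

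What the reply does not answer is that withdrawal is from the study as a whole, that no calls-or-records-only status exists, and that no registry back-up covers hospitalizations or exacerbations.

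**Conclusion.** The point holds as a gap in the follow-up rules. The protocol does not separate ending procedures from ending event follow-up, and two of its three examples of grounds for withdrawal can result from disease progression. Hospitalizations and self-reported exacerbations after such a withdrawal may be missed selectively. Deaths are at risk only if the Index searches leave these participants out, which 6.7.1.2 leaves open.

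The size is unknown: it depends on how often investigators use the rule and on what happens to those participants afterwards. The mortality power figures are a worst case under stated assumptions and not an estimate. The protocol's own power figure reproduces, and no stated power figure is wrong on this account. The change is still worth making during the study, because events not asked about at the time may not be recoverable later.

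**What to change.** 1. In 5.3.6.1, state that impairment or institutionalization ends clinic procedures only. Within the participant's consent and local rules, quarterly calls (by proxy if needed) and hospital-record retrieval continue.
2. In 6.7.1.2, state that both the annual search and the completion query include participants withdrawn by the investigator, within their consent.
3. Keep full withdrawal for cases where contact itself is unsafe or unethical.

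**Cost.** Protocol and consent wording. The calls, record requests and Index searches already exist as study procedures. Some data will be proxy-reported, which may be less accurate for milder exacerbations, and local rules may limit contact with prisoners. Sample size and stated power need no change.

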5.3.6.2. Participant Request

Participants may withdraw at any time for any reason. At the time of withdrawal participants can either 1) decline to provide any more data or specimens to the study but allow use of previously collected data and/or specimens, 2) withdraw all their data from study databases and request that any stored samples be destroyed, or 3) withdraw some portion of the data collected (i.e., participants may withdraw specimens but not exam data or vice versa).

5.3.6.3. Participant exit interview

If a participant chooses to withdraw from the SPIROMICS study, the study coordinator will conduct an exit interview to determine the disposition of the participants' study data (see Section 5.3.6). The coordinator will also provide the participant with any clinically relevant study results or establish how the participant would like to be contacted if relevant results become available in the future. The participant may decline to participate in the exit interview, in which case the consent in place at the time of study withdrawal will be used to determine the status of the participant's data.

6. Study Procedures

